2.0 Goals

2.1 Primary Objective:

To estimate and compare treatment failure-free rate at 40 weeks from randomization of patients with unresectable/metastatic clear cell Renal Cell Carcinoma (ccRCC) receiving one of the following regimens:

- Arm A: Pazopanib 800mg daily plus intravenous (IV) ascorbic acid 1g/kg 3 times/week.
- Arm B: Pazopanib 800mg daily

2.2 Secondary Objective:

- 2.21 To estimate and compare the overall survival (OS) in patients receiving pazopanib with or without IV ascorbic acid
- 2.22 To estimate and compare the progression-free survival (PFS) in patients receiving pazopanib with or without IV ascorbic acid
- 2.23 To estimate and compare the overall response rate (ORR) in patients receiving pazopanib with or without IV ascorbic acid
- 2.24 To estimate and compare the duration on pazopanib treatment in patients receiving pazopanib with or without IV ascorbic acid
- 2.25 To assess the adverse events (AE) profile and safety of each treatment arm using the CTCAE

2.3 Correlative Research

2.31

Correlation between 5mC, 5hmC and H3K27me3 expression (as determined by IHC), as well as MeDIP/hMeDIP seq, and response to combination of IV ascorbic acid and pazopanib.

2.32

Correlation between iron content in tumor microenvironment (as determined by Prussian blue staining) and response to combination of IV ascorbic acid and pazopanib.

- 2.33 Correlation between HIF-1 α and HIF-2 α expression (as determined by IHC) and response to combination of IV ascorbic acid and pazopanib.
- 2.34 Correlation between GLUT1 expression (as determined by IHC) and response to combination of IV ascorbic acid and pazopanib.
- 2.35 Correlation between PDL1 expression (as determined by IHC) and response to combination of IV ascorbic acid and pazopanib.

3.0 Patient Eligibility

3.1 Inclusion Criteria

- 3.11 Age \geq 18 years
- 3.12 Histological confirmation of clear cell renal cancer.
- 3.13 Documented metastatic or unresectable disease and at least one measurable lesion by RECIST criteria. NOTE: Nephrectomy or ablation of the primary tumor is allowed prior to enrollment.
- 3.14 No prior systemic therapy for clear cell renal cancer; or have progressed after immunotherapy such as ipilimumab plus nivolumab in the first line. Other immunotherapies (e.g. interleukin-2) or additional lines of immunotherapy may be allowed after discussion with the Principal Investigator.
- 3.15 ECOG Performance Status (PS) 0, 1 or 2.
- 3.16 The following laboratory values obtained \leq 21 days prior to randomization:
 - ANC \geq 1500/mm³
 - PLT \geq 100,000/mm³
 - Hgb \geq 9.0 g/dL NOTE: Subjects may not have had a transfusion \leq 7 days of randomization
 - Total Bilirubin \leq 1.5 x ULN.
 - NOTE: For bilirubin elevation 1 to 1.5x ULN, ALT above 1.5 x ULN (upper limit of normal) is not permitted.
 - NOTE: For bilirubin elevation 1 to 1.5x ULN, AST above 1.5 x ULN (upper limit of normal) is not permitted.
 - Alanine amino transferase (ALT) <2.5 X ULN, with normal bilirubin. NOTE: Concomitant elevations in bilirubin and ALT above 1.5 x ULN (upper limit of normal) is not permitted.
 - Aspartate aminotransferase (AST) <2.5 X ULN, with normal bilirubin. NOTE: Concomitant elevations in bilirubin and AST above 1.5 x ULN (upper limit of normal) is not permitted.

- Creatinine ≤ 1.5 mg/dl OR creatinine > 1.5 mg/dl, estimated creatinine clearance must be ≥ 55 mL/minute by CockcroftGault formula:

Cockcroft-Gault Equation:

Creatinine clearance for males =
$$\frac{(140 - \text{age})(\text{weight in kg})}{(72)(\text{serum creatinine in mg/dL})}$$

Creatinine clearance for females =
$$\frac{(140 - \text{age})(\text{weight in kg})(0.85)}{(72)(\text{serum creatinine in mg/dL})}$$

- INR and aPTT $\leq 1.5 \times$ ULN. NOTE: This applies only to patients who are not receiving therapeutic anticoagulation; patients receiving therapeutic anticoagulation should be on a stable dose.

3.17 Individuals of non-childbearing potential, *or* individual of childbearing potential with negative serum pregnancy test ≤ 7 days prior to randomization and willing to practice total abstinence or use a highly effective method of contraception, as outlined in item “c” below:

- Non-childbearing potential (i.e., physiologically incapable of becoming pregnant), including any female individual who has had the following:
 - A hysterectomy
 - A bilateral oophorectomy (ovariectomy)
 - A bilateral tubal ligation
 - Is post-menopausal

NOTE: Subjects not using hormone replacement therapy (HRT) must have experienced total cessation of menses for ≥ 1 year and be greater than 45 years in age, OR, in questionable cases, have a follicle stimulating hormone (FSH) value > 40 mIU/mL and an estradiol value < 40 pg/mL (< 140 pmol/L).

Subjects using HRT must have experienced total cessation of menses for ≥ 1 year and be greater than 45 years of age OR have had documented evidence of menopause based on FSH and estradiol concentrations prior to initiation of HRT

- Childbearing potential, including any individual who has had a negative serum pregnancy test, ≤ 7 days prior to randomization.
- Agrees to use adequate contraception. Acceptable contraceptive methods, when used consistently and in accordance with both the product label and the instructions of the physician, are as follows:
 - Complete abstinence from sexual intercourse for 14 days before exposure to investigational product, through the

dosing period, and for at least 21 days after the last dose of investigational product;

- Oral contraceptive, either combined or progestogen alone
- Intrauterine device (IUD) or intrauterine system (IUS) with a documented failure rate of less than 1% per year;
- Male partner sterilization (vasectomy with documentation of azoospermia) prior to the female subject's entry into the study, and this male is the sole partner for that subject;
- Double barrier method: condom and an occlusive cap (diaphragm or cervical/vault caps) with a vaginal spermicidal agent (foam/gel/film/cream/suppository).

3.18 Provide informed written consent.

3.19 Willing to provide archive tissue samples for correlative research purposes (See Sections 4.0, 6.0 and 17.0.)

- 3.28 Other active malignancy ≤ 5 years prior to randomization. EXCEPTIONS: Nonmelanoma skin cancer or carcinoma-in-situ of the cervix, or cancers with low metastatic potential (e.g. Gleason score 6 prostate cancer) treated with curative therapy. NOTE: If there is a history or prior malignancy, they must not be receiving other specific treatment for their cancer.
- 3.29a History or clinical evidence of central nervous system (CNS) metastases or leptomeningeal carcinomatosis, except for individuals who have previously treated CNS metastases, are asymptomatic, and have had no requirement for steroids or anti-seizure medication for ≤ 6 months prior to randomization.. Note: Screening with CNS imaging studies (computed tomography [CT] or magnetic resonance imaging [MRI]) is required only if clinically indicated or if the subject has a history of CNS metastases.
- 3.29b Clinically significant gastrointestinal abnormalities that may increase the risk for gastrointestinal bleeding including, but not limited to:
- Active peptic ulcer disease,
 - Known intraluminal metastatic lesion/s with risk of bleeding,
 - Inflammatory bowel disease (e.g. ulcerative colitis, Crohn's disease), or other gastrointestinal conditions with increased risk of perforation,
 - History of abdominal fistula, gastrointestinal perforation, or intra-abdominal abscess ≤ 28 days prior to randomization,
 - Clinically significant gastrointestinal abnormalities that may affect absorption of investigational product including, but not limited to:
 - Malabsorption syndrome
 - Any prior major resection of the stomach or small bowel.
- 3.29c Corrected QT interval (QTc) > 480 msec using Bazett's formula.

- 3.29d Receiving any medications or substances with risk of Torsades de Pointes (see Appendix IV). Note: Medications or substances on the list “Drugs with Risk of Torsades de Pointes” are prohibited. Medications or substances on the list “Drugs with Possible or Conditional Risk of Torsades de Pointes” may be used while on study with extreme caution and careful monitoring.
- 3.29e Treatment with any of the following anti-cancer therapies \leq 14 days prior to randomization:
- radiation therapy
 - surgery or tumor embolization
 - chemotherapy, immunotherapy
 - biologic therapy
 - investigational therapy
 - hormonal therapy
- 3.29f Prior autologous or allogeneic organ or tissue transplantation.
- 3.29g Elective or planned major surgery to be performed during the course of the trial.
- 3.29h Receiving any medications or substances that are strong or moderate inhibitors of CYP3A4 (for a listing of medications or substances see Appendix V) Use of strong or moderate inhibitors are prohibited \leq 7 days prior to randomization.
- 3.29i Receiving any medications or substances that are inducers of CYP3A4 (for a listing of medications or substances see Appendix V). Use of inducers are prohibited \leq 7 days prior to randomization.
- 3.29j Glucose-6-phosphate dehydrogenase (G6PD) deficiency (i.e. below normal limits).
- 3.29k End-stage renal disease (estimated GFR <55 ml/min/BSA), unless the estimated creatinine clearance by Cockcroft Gault is ≥ 55 ml/min prior to randomization.
- 3.29l History of calcium oxalate stones.
- 3.29m History of iron overload.
- 3.29n Unable to swallow oral medications.
- 3.29o History of myocardial infarction ≤ 6 months, current symptomatic CHF or LVEF $<40\%$ or $>$ grade 2 diastolic dysfunction, with no symptoms or signs of heart failure.

4.0 Test Schedule

Cycle length = 28 days.

Tests and procedures	Active Monitoring Cycle length = 28 days +/- 7 day window for study visits and tests. ⁵				
	≤21 days prior to randomization	Prior to each new cycle (≤7 days)	Prior to 3 rd and subsequent odd cycles (5, 7, 9, etc.)	At PD, withdrawal, removal, or end of protocol treatment	Observation (Clinical follow-up)
Informed Consent	X				
History and exam, wt., ECOG PS	X	X		X	X
Height	X				
Adverse event assessment	X	X ⁶		X	X
Echocardiogram (2D M-Mode)	X ⁸				
Hematology: CBC/ differential	X	X ⁵		X	X
Chemistry: SGOT (AST), alk phos, T. bili, creatinine, calcium, phos, glucose, Na, K, ALT, GFR, LDH ¹¹	X	X ^{4,5}		X	X
G6PD test	X ^{R, 9}				
Urinalysis	X			X	
Thyroid function test (TSH)	X		X		
Coagulation test: INR, APTT	X				
Tumor measurement	X ¹		X ¹		X ^{1, 10}
CT/MRI brain, if needed (See Section 3.29a)	X		X		
Bone scan ¹²	X		X		
ECG	X		X		
Pregnancy test (serum)	X ²				
Mandatory archival tissue collection (see Section 17.2)	X ^{R, 7}				
Patient Medication Diary (Appendix II)		X ³		X ³	

¹ CT chest, abdomen, and pelvis with IV contrast. If unable to receive IV contrast, MRI abdomen/pelvis with contrast and CT chest without contrast are acceptable. Use same imaging method throughout the study.

- ² For individuals of childbearing potential only. Must be done ≤ 7 days prior to randomization.
- ³ The diary must begin the day the patient starts taking the medication and must be completed per protocol and returned to the treating institution every 4 weeks.
- ⁴ For ARM- A (ascorbic acid group) only: Draw at baseline then weekly for Cycle 1, then for subsequent cycles on Day 14 and Day 28. For ARM B only: draw at baseline then once every cycle.
- ⁵ Labs do not have to be repeated prior to Cycle 1 if they were done ≤ 5 days prior to cycle.
- ⁶ Starting with Cycle 2, AE's for Cycle 1 are assessed prior to the beginning of Cycle 2 and are recorded under Cycle 1 AE, following this format for all subsequent cycles.
- ⁷ Receipt of archival tumor tissue (if available) is not required for study randomization and initiation of therapy. . However, it is mandatory to receive the required tissue ≤ 30 days from registration.
- ⁸ Echocardiogram done ≤ 6 months prior to randomization is acceptable.
- ⁹ G6PD = Glucose-6-phosphate dehydrogenase. If G6PD is found to be below normal limits, patient will be ineligible for the trial. If below normal limits, the test can be repeated up to two additional times. One normal result is sufficient for eligibility if done within 6 months prior to randomization (does not need to be repeated within the 21-day window).
- ¹⁰ Imaging frequency is every 8 weeks or as clinically indicated, until progression or 2 years since study randomization, whichever is first, or per treating physician discretion.
- ¹¹ LDH = Lactate dehydrogenase. Include with chemistries at baseline and during treatment.
- ¹² For patients with a history of bone metastases or for whom there is clinical suspicion of bone metastases at study entry.
- ¹³ If the urinalysis prior to randomization indicates proteinuria, urine protein/ Cr or 24hr urine protein would need to be monitored as clinically indicated throughout the study period. Pazopanib dose modification based on significant proteinuria to be followed, as stated in section 8.12.
- ^R Research funded (see Section 19.0).

5.0 Stratification Factors:

- MSKCC risk category (Favorable risk vs. Intermediate risk vs. Poor risk. See Appendix VI for MSKCC risk score.)
- Sarcomatoid differentiation (Yes vs. No)

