10.54 Case Report Forms - Academic and Community Cancer Research United (ACCRU)

Submit the following AEs not specified in Section 10.5 (paper or electronic, as applicable)

10.541 Grade 2 AEs deemed *possibly, probably, or definitely* related to the study treatment or procedure.

10.542 Grade 3 and 4 AEs regardless of attribution to the study treatment or procedure.

10.543 Grade 5 AEs (Deaths)

10.5431 Any death within 30 days of the patient’s last study treatment or procedure regardless of attribution to the study treatment or procedure.

10.5432 Any death more than 30 days after the patient’s last study treatment or procedure that is felt to be at least possibly treatment related must also be submitted as a Grade 5 AE, with a CTCAE type and attribution assigned.

- 10.55 Refer to the instructions in the Case Report Forms (CRF) Packet (or electronic data entry screens, as applicable) regarding the submission of late occurring AEs following completion of the Active Monitoring Phase (i.e., compliance with Test Schedule in Section 4.0).

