13.0 Treatment/Follow-up Decision at Evaluation of Patient

13.1 Patients who are CR, PR, or SD will continue treatment per protocol up to a maximum of 10 cycles or until PD whichever is first. After 10 cycles of treatment, treatment may be continued off study per physician discretion. Patients who are CR, PR, or SD after 10 cycles will move to Observation Phase of the trial (see section 13.2).

13.2 Observation:

Patients who complete protocol treatment, or discontinue protocol treatment due to unacceptable toxicity or other complicating disease, will be followed every 8 weeks (+/- 7 days) for a maximum of 2 years from the registration in the Observation Phase per Section 4.0 of the protocol.

13.3 Event Monitoring:

Patients who develop PD, choose alternative therapy, refuse treatment or refuse to be followed in observation at any time will go to the Event Monitoring phase and be followed every 6 months (+/- 30 days) for a maximum of 3 years from registration per Section 18.0 of the protocol. Treatment options for these patients are at the discretion of the treating physician.

13.4 Patients who develop PD in the CNS only should receive whole brain radiotherapy (WBRT) and continue treatment on study after completion of WBRT.

13.5 A patient is deemed *ineligible* if after registration, it is determined that at the time of registration, the patient did not satisfy each and every eligibility criteria for study entry. The patient may continue treatment off-protocol at the discretion of the physician as long as there are no safety concerns, and the patient was properly registered. The patient will go directly to the event-monitoring phase of the study (or off study, if applicable).

- If the patient received treatment, all data up until the point of confirmation of ineligibility must be submitted. Event monitoring will be required per Section 18.0 of the protocol.
- If the patient never received treatment, on-study material must be submitted. On-study material and the Off Treatment Form must be submitted. No further data submission is necessary.

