16.32 Definitions and Analyses of Secondary Endpoints

16.321 Overall Survival

Survival time is defined as the time from randomization to death due to any cause. Patients who are alive will be censored for death at the time of last known alive. All patients meeting the eligibility criteria that have signed a consent form and begun treatment will be considered evaluable for estimation of the survival distribution. The distribution of survival time will be estimated using the method of Kaplan-Meier and be compared using log rank tests.

16.322 Progression Free Survival

Progression Free Survival is defined as the time from start of study therapy to documentation of disease progression or death, whichever comes first. Patients who are still alive and have not progressed will be censored for progression at the time of the last tumor assessment. All patients meeting the eligibility criteria that have signed a consent form and begun treatment will be considered evaluable for estimation of the survival distribution. The progression free survival distribution will be estimated using the Kaplan-Meier method.

16.323 Overall Response Rate

A tumor response is defined to be a CR or PR noted as the objective response (according to RECIST v. 1.1) All patients meeting the eligibility criteria who have signed a consent form and have begun treatment will be evaluable for response. The best objective response rates between the two arms will be compared using a Chi-Square test.

16.324 Duration of time on pazopanib

Duration of time on pazopanib is defined as the time from initial dose of

pazopanib until the date the patient is considered off-treatment for pazopanib or death, whichever comes first. Only patients received at least 1 dose of pazopanib will be considered evaluable for this analysis. The time on pazopanib will be described using descriptive statistics.

16.325 Adverse events:

As per NCI CTCAE version 4.0, the term toxicity is defined as adverse events that are classified as either “possibly,” “probably,” or “definitely related” to study treatment. The maximum grade for each type of toxicity will be recorded for each patient, and frequency tables will be reviewed to determine toxicity patterns within patient groups. In addition, we will review all adverse event data that is graded as 3, 4, or 5 and classified as either “unrelated” or “unlikely to be related” to study treatment in the event of an actual relationship developing.

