Adverse events and toxicities will be evaluated using all patients who have received any study treatment as well as summarizing those who have been included in the efficacy analyses. The overall adverse event rates for grade 3 or higher adverse events will be compared using Chi-Square tests between the 2 treatment arms.

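### Arm A has 22 scheduled on-treatment chemistry draws to Arm B's 10, and the planned chi-square on grade 3 or higher adverse events makes no allowance for it

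*Combined protocol and SAP*

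**What the plan says.** Section 4.0, footnote 4, gives the two arms different chemistry schedules. Arm A: "Draw at baseline then weekly for Cycle 1, then for subsequent cycles on Day 14 and Day 28". Arm B: "For ARM B only: draw at baseline then once every cycle". The panel covers AST, ALT, bilirubin, creatinine, electrolytes and glucose. Section 10.53 lists ten solicited adverse event terms, and four of them (bilirubin, AST, ALT and creatinine increased) come from this panel. Hematology and the adverse event assessment itself are scheduled alike in both arms.

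Mid-cycle results enter the record. Footnote 6 of the same table says that "AE's for Cycle 1 are assessed prior to the beginning of Cycle 2 and are recorded under Cycle 1 AE", and likewise for later cycles. Section 10.54 collects "Grade 3 and 4 AEs regardless of attribution to the study treatment or procedure".

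For the analysis, section 16.325 states: "The maximum grade for each type of toxicity will be recorded for each patient". It then adds: "The overall adverse event rates for grade 3 or higher adverse events will be compared using Chi-Square tests between the 2 treatment arms". I found nothing in sections 16.3 to 16.325 that restricts the comparison to a common schedule, separates laboratory from clinical events or adjusts for the number of assessments. Neither a significance level nor sidedness is given for this test.

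**The concern.** A chemistry abnormality without symptoms is seen only if blood is drawn while it is present. Looking more often at one arm finds more short-lived abnormalities there, even when true toxicity is equal. Both summaries in 16.325 move in one direction with extra looks: another draw can raise a patient's maximum grade or turn a patient without a grade 3 event into one with such an event, but it cannot do the reverse.

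Objective 2.25 is the adverse event and safety profile of each arm, and the first hypothesis in section 1.4 includes better tolerance with ascorbic acid. An excess in Arm A that comes from the draw schedule could be reported as added harm, or could hide a real gain in tolerance.

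**Working it through.** **1. Count of draws.** The plan states no total, so there is no figure of its own to reproduce. Inputs: the two schedules in footnote 4; "Cycle length = 28 days" (section 4.0), so weekly means 4 draws in Cycle 1; and section 13.1, under which patients with CR, PR or SD "will continue treatment per protocol up to a maximum of 10 cycles or until PD whichever is first".

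- Arm A: 4 + 9 × 2 = 22
- Arm B: 10 × 1 = 10
- Ratio: 22 / 10 = 2.2. With baseline the counts are 23 and 11.
- Cumulative for patients who stop earlier: 4 vs 1 after Cycle 1, 8 vs 3 after Cycle 3, 14 vs 6 after Cycle 6.

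**2. Illustration by chance per draw.** Assumptions, none of them from the documents: each draw independently shows a grade 3 or higher value with probability p, the same in both arms; patients complete 10 cycles; a share s of patients has some other grade 3 or higher event found equally in both arms; the test is an uncorrected Pearson chi-square at two-sided 5%. The 41 per arm is from section 16.21.

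Chemistry events alone: 1 − (1 − p)^22 in Arm A and 1 − (1 − p)^10 in Arm B.

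- p = 1%: 1 − 0.99^22 = 19.8%; 1 − 0.99^10 = 9.6%
- p = 2%: 1 − 0.98^22 = 35.9%; 1 − 0.98^10 = 18.3%

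Any grade 3 or higher event: 1 − (1 − s) × (1 − chemistry rate). For s = 40% and p = 1%, Arm A is 1 − 0.6 × 0.802 = 51.9% and Arm B is 1 − 0.6 × 0.904 = 45.7%. Rejection probabilities come from exact enumeration of the two binomials.

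| Other events, s | p = 1%: A vs B | Rejects | p = 2%: A vs B | Rejects |
|---|---|---|---|---|
| none (chemistry only) | 19.8% vs 9.6% | 27% | 35.9% vs 18.3% | 44% |
| 40% | 51.9% vs 45.7% | 10% | 61.5% vs 51.0% | 18% |
| 60% | 67.9% vs 63.8% | 7% | 74.4% vs 67.3% | 11% |

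With equal observed rates near those in the 40% row, the same test rejects about 6% of the time.

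**3. Illustration by duration.** Suppose instead that an affected patient has one chemistry event of D days, placed uniformly within the 280 treatment days, with draws on their nominal days. For D below 28, Arm B detects it with probability 9D / (280 − D). For D up to 7, Arm A detects it with probability 21D / (280 − D); from D = 14 Arm A always detects it.

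| D (days) | Arm A | Arm B |
|---|---|---|
| 3 | 63/277 = 23% | 27/277 = 10% |
| 7 | 147/273 = 54% | 63/273 = 23% |
| 14 | 100% | 126/266 = 47% |
| 21 | 100% | 189/259 = 73% |
| 28 or more | 100% | 100% |

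If 10% to 30% of patients have such an event and s = 40%, the excess in Arm A is 0.6 × share × (detection in A − detection in B):

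- 7 days: 0.6 × 0.10 × 0.307 = 1.8 points, up to 5.5 points at 30%
- 14 days: 0.6 × 0.10 × 0.526 = 3.2 points, up to 9.5 points at 30%
- 28 days or more: 0

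The chance of a significant result against Arm A rises from about 2.8% to 4–8% for 7-day events and 5–15% for 14-day events.

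**The case against.** The strongest reply is that the effect on the planned test may be small. That test pools all grade 3 or higher events. Symptoms and hematology are not touched by footnote 4 and dilute the gap. Independence between draws is close to a worst case, since it requires an abnormality to be gone a week later; anything lasting 28 days is found in both arms. Section 8.14 requires weekly liver tests in both arms once ALT exceeds three times the upper limit. All of this stands as a limit on size. It does not remove the mechanism: the weekly liver tests begin only after a rise has been found, so they do not equalize first detection.

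Three stronger readings are tempting, and the documents do not support them.

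- A reader might infer that Arm A must show more of every chemistry event. Section 15.26 warns of false-negative bilirubin and glucose results during an infusion or in the 24 hours after it, and Arm A is infused three times a week, so the direction for those terms is uncertain. ALT, AST and creatinine are not named in that warning. Earlier detection may also prompt action before a value reaches grade 3.
- A reader might take the 27% and 44% in the chemistry-only row as the error rate of the planned comparison. Section 16.325 specifies a test on overall rates, not on laboratory events alone.
- A reader might infer that extra draws bias the primary endpoint, because going off treatment for an adverse event counts as failure (section 16.11). The creatinine rules mainly hold, reduce or resume treatment, and a first isolated ALT above eight times the upper limit interrupts pazopanib; it does not end it (sections 8.12, 8.14, 8.21). Extra draws could cause or prevent discontinuations, and nothing in the documents allows either to be quantified.

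**Conclusion.** The point holds in limited form. The counts of 22 and 10 follow directly from the schedule for a patient who completes 10 cycles. As written, the comparison in 16.325 can be biased against Arm A through chemistry-defined events shorter than 28 days, most clearly ALT, AST and creatinine.

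The size cannot be established from the documents. Under the assumptions in step 2 with 40% other events, equal true toxicity appears as a difference of about 6 points (p = 1%) or 11 points (p = 2%), with rejection at about 10% or 18% instead of about 6%. Under the duration model the excess runs from zero to 9.5 points. The per-draw rates, durations, share of other events and 5% level are all assumptions.

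This is a secondary safety comparison. Neither the TFF40 decision rule nor the stopping rule in 16.42, which counts events in each arm separately, uses it.

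**What to change.** In section 16.325:

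- Keep the table based on all draws.
- Compare clinical and chemistry-defined grade 3 or higher events separately between arms.
- Add a sensitivity comparison of chemistry-defined events limited to the once-per-cycle draw common to both arms, and list separately the events found only on Arm A's extra draws.
- State in advance that any Arm A excess in laboratory events will be read against this sensitivity analysis. Once chemistry events stand alone, clinical events no longer dilute the difference in detection, so the all-draws laboratory comparison should not be read by itself.

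The cost is a few lines of text and one or two extra tables, from data already collected. The shared-draw analysis has its own weakness: an Arm A abnormality found and acted on mid-cycle may have resolved by the shared draw, while the same event in Arm B may still be present, so the analysis can err in Arm A's favor. It should therefore supplement the planned comparison and not replace it. The safety monitoring schedule stays as it is.
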